## **7. PLANNED ANALYSIS**

The format of the listings and tables will follow the BI guideline "Standards for Reporting of Clinical Trials and Project Summaries" (9).

The individual values of all patients will be listed, sorted by dose group, patient number and visit. AE listings will be sorted by assigned treatment (see [Section 7.8.1](#) for details). The listings will be contained in an Appendix of the CTR.

For End-Of-Text tables, the set of summary statistics is: N / Mean / Standard Deviation (SD) / Min / Median/ Max. For tables that are provided for endpoints with some extreme data, median, quartiles and percentiles are preferred to mean, standard deviation, minimum and maximum. In general, means, medians, and percentiles are presented to one more decimal place than the raw data and SDs are presented to two more decimal places than the raw data. Minima and Maxima are presented to the same number of decimal places as the raw data.

Disposition of the patient population participating in the trial will be analyzed by treatment and presented by the categories in the standard CRF groups and presented in the clinical trial report as a frequency-distribution.

For categorical data, tabulations of frequencies will include all defined categories even if there is no count in a category. Tabulations of frequencies will display the number of observations in a category as well as the percentage (%) relative to the number of patients in the respective treatment group. All patients in the respective patient set are used whether they have non-missing values or not, unless otherwise specified. Percentages will be rounded to one decimal place. The category missing will be displayed only if there are missing values.

If applicable, conversion from days to weeks, months and years will be as follows:

- weeks = days  $\div$  7
- months = 12  $\times$  days  $\div$  365.25
- years = days  $\div$  365.25.

### **7.1 DEMOGRAPHIC AND OTHER BASELINE CHARACTERISTICS**

Only standard descriptive statistics and summary tables are planned for this section of the report. Data will be summarized by treatment group and a "total" column will be included in the summary table.

### **7.2 CONCOMITANT DISEASES AND MEDICATION**

Only descriptive statistics are planned for this section of the report.

Concomitant diseases (i.e., baseline conditions) will be coded similarly as AEs using the most recent version of MedDRA. A summary of concomitant diseases will be provided by

treatment group, System Organ Class (SOC) and Preferred Term (PT). Concomitant diseases which are present at start of the study will be descriptively summarized by treatment.

A medication/therapy will be considered concomitant to treatment if it (1) is ongoing at the start of randomized trial treatment or (2) starts within the on-treatment phase (see [Section 6.1](#) for a definition of study analysis phases). A medication/therapy will be considered as prior medication/therapy, if the end date of the medication/therapy is at any time prior to the start of randomized trial treatment.

Concomitant therapies (CTs) are coded according to WHO Drug Dictionary. CTs will be classified according to the Anatomical Therapeutic Chemical (ATC) classification system. The third ATC level will be used to categorize CTs by therapy type. In situations where a medical product may be used for more than one equally important indication, there are often several classification alternatives. As appropriate, patients receiving CTs with more than one possible ATC level-three category will be counted more than once and footnote will clarify this possible multiple counting in tables. The most current WHO Drug Dictionary version will be used.

## **7.3 TREATMENT COMPLIANCE**

### **7.3.1 Compliance**

Only descriptive statistics are planned for this section of the report. Treatment compliance is the percentage of tablets that were correctly taken by a patient, and is calculated at Weeks 1, 2, 4, and 6 (EOT) as follows, based on the CTP's flow chart:

$$\text{Treatment compliance (\%)} = \frac{\text{Number of doses actually taken}}{\text{Number of doses which should have been taken as directed by investigator}} * 100$$

The cumulative treatment compliance during the entire treatment period is derived using the following examples:

For completers: if a patient's observed treatment compliance rates are 80%, 81%, 82%, 83% at Weeks 1, 2, 4, and 6, then the cumulative treatment compliance percent =  $(.8*1 + .81*1 + .82*2 + .83*2)/6*100 = 81.83\%$ .

For early discontinued patient: if a patient's observed treatment compliance rates are 80% at Week 1, 81% at Week 2, 82% at Week 4, 50% at eEOT, then the cumulative treatment compliance rate =  $(0.80*1 + 0.81*1 + 0.82*2 + 0.5*((\text{eEOT date} - \text{drug start date} + 1)/7 - 4))/((\text{eEOT date} - \text{drug start date} + 1)/7) * 100\% = 74.3\%$  if the quantity (eEOT date - drug start date + 1) is assumed to be 36 days.

If at a particular visit a participant did not return the trial drug kits, then the compliance at that visit is zero.

Treatment compliance will be summarised overall and by visit for the FAS using descriptive statistics (N, mean, SD, minimum, median, maximum). The number and percentage of

patients with the following overall compliance categories will also be presented overall and by visit:

- "<80% of planned",
- "80 to <=100% of planned",
- ">100% of planned",
- missing.

[REDACTED]

[REDACTED]

| [REDACTED]

[REDACTED]

[REDACTED]

[REDACTED]

[REDACTED]

[REDACTED]

[REDACTED]

## **7.4 PRIMARY OBJECTIVE ANALYSIS**

### **7.4.1 Main analysis**

The primary endpoint is the change from baseline to Week 6 in MADRS total score. Baseline MADRS total score is the last non-missing value recorded prior to first dose of trial medication and is typically recorded at Visit 2. If data from Visit 2 are missing, the value recorded at Visit 1 will be considered the baseline value. The investigator reported MADRS total scores will be used for the primary analysis.

Total scores as delivered by the vendor will be re-calculated and in case of discrepancies, the re-calculated scores will be used for analysis.

The primary analysis of the primary endpoint will use a hypothetical estimand. The hypothetical approach focuses on the treatment effect assuming all patients remained adherent to the assigned trial medication and the trial protocol, i.e., took study drug as directed. The primary analysis of the primary endpoint will include all data collected while on treatment, which is defined as the time from the date of the first dose of trial medication until the date of the last dose of trial medication plus 7 days (3 times the estimated elimination half-life). Any data collected after any intercurrent event listed in [Table 3](#) will be censored and not included in the primary analysis. Data from participants assigned to the quetiapine arm will not be included in the primary analysis.

The Multiple Comparison Procedures and Modeling (MCPMod) approach ([10, 11](#)) is implemented in two main stages: (1) trial design stage; (2) trial analysis stage. The procedures for the trial design stage, including the selection of candidate models covering a suitable range of dose-response shapes and sample size and power calculations are provided in the CTP Sections 7.2.2 and 7.5. The procedures for the trial analysis stage are specified below. FAS is used for the primary analysis of the primary efficacy endpoint.

#### MMRM analysis

The change from baseline in MADRS total score at Week 6 for each dose group as well as the corresponding variance-covariance matrix will be estimated by an MMRM model including the fixed categorical effects of treatment at each visit, concomitant psychotherapy use (yes vs. no), and the fixed continuous effect of baseline MADRS total score at each visit. Visit will be treated as a repeated measure with an unstructured covariance matrix used to estimate within patient error variability. The Kenward-Roger approximation will be used to estimate the denominator degrees of freedom and adjust standard errors. Significance tests will be based on least-squares (LS) means using a two-sided  $\alpha = 0.1$  (two-sided 90% confidence intervals (CIs)). Analyses will be implemented using SAS 9.4 PROC MIXED.

More specifically, the change in MADRS total score from baseline at Visits 3, 4, 6, and 8 (Weeks 1, 2, 4, and 6) will be evaluated using an MMRM accounting for the following sources of variation: ‘concomitant psychotherapy use’, ‘treatment\*visit’ interaction, and ‘baseline MADRS total score\*visit’ interaction as fixed effects, and visit as a repeated measure within each patient. The methods described in [Section 10.1.1](#) will be utilized to resolve model non-convergence.

The following SAS code will be used to run the MMRM model, with some modifications if necessary:

```
PROC MIXED DATA=indata cl method=reml;
  CLASS visit trt(REF='placebo') ptno conPTuse;
  MODEL aval = conPTuse visit*trt base*visit / ddfm=kr s;
  REPEATED visit / subject= ptno type=un r rcorr;
  LSMEANS visit*trt / pdiff=all om cl alpha=0.10 slice=visit;
RUN;
```

Results of the MMRM (N, LS means, standard errors, and 90% CIs per dose group) will be presented in tables and displayed graphically.

Descriptive summaries for observed values and change from baseline in MADRS total score at Weeks 1, 2, 4 and 6 will be presented by treatment arm, including the quetiapine arm. The frequency and proportion of participants reporting each response category for each MADRS item at baseline and up to Week 6 will also be displayed.

#### MCPMod Analysis

The adjusted mean estimates of the change from baseline at Week 6 for each dose and their estimated variance-covariance matrix from the MMRM model will be used in the trial analysis stage. Then, the multiple pair-wise comparison procedure will be implemented using the optimal contrast tests which control the family-wise type I error rate at one-sided  $\alpha = 0.10$ .

The basic shape of each of the models to be tested must be predefined in the trial analysis stage. The following candidate models were selected based on healthy volunteer data to cover a plausible and diverse range of dose response patterns for the trial medication.

- Emax1: 50% of the maximum effect is achieved at 25 mg; corresponding to the assumed true ED50 = 25 mg.
- Emax2: 70% of the maximum effect is achieved at 5 mg; corresponding to a drug effect achieved mainly with low doses, ED50 = 2.14 mg.
- Sigmax: 50% of the maximum effect is achieved at 25 mg, and
- 90% of the maximum effect is achieved at 75 mg; corresponding to a more flexible model of the assumed true ED50 = 25 mg.
- Exponential: 5% of the maximum effect is achieved at 25 mg; corresponding to a drug effect achieved mainly at higher doses.
- Linear: No parameter assumptions required. Corresponding dose response is linear.

For the MCPMod test, the optimal contrasts corresponding to the candidate models are calculated as in the trial design stage (using the R-function optContr using weights proportional to the sample size of each dose group) and are shown in [Table 7](#) below. These contrasts will be updated using the expected model means from the candidate set and the

estimated variance-covariance matrix from the data. The final contrasts will be presented in the CTR.

Table 7 Optimal contrast coefficients

Model	Optimal Contrast Coefficients for Dose				
	0	5mg	25mg	75mg	125mg
Linear	-0.643	-0.161	-0.073	0.146	0.731
Emax1	-0.772	-0.119	0.084	0.235	0.572
Emax2	-0.867	0.076	0.178	0.201	0.413
Sigmax	-0.731	-0.188	0.055	0.266	0.597
Exponential	-0.545	-0.150	-0.127	0.007	0.815

Proof of concept is established if at least one dose-response model is statistically significant, i.e., the null hypothesis of a flat dose-response curve for change from baseline in MADRS total score at Week 6 is rejected, indicating a benefit of at least one BI 1358894 dose over placebo.

Once the significance of a dose-response signal is established, the dose-response profile and the target dose can be estimated using the model averaging method.

The selected dose-response model(s) is re-fitted to the data without any parameter assumptions to generate a set of new estimates of the model parameters from the data. The final dose-response model is obtained via the weighted model averaging of the significant models ( $p\text{-value} < 0.10$ ) based on Akaike Information Criterion (AIC) (the smaller the AIC value the better the model fit). The weights for each significant model ( $M_k$ ) are given by,

$$w(M_k) = \frac{\exp(-0.5 * AIC(M_k))}{\sum_{i=1}^K \exp(-0.5 * AIC(M_i))}$$

where  $AIC(M_k)$  is the AIC for model  $M_k$ .

Test statistics and p-values will also be displayed for different dose-response models. Figures and tables will be displayed for the MCPMod modeling.

[figure not shown]
The following displays are planned:

- Table of the contrast coefficients per dose group and candidate model, together with the MCPMod test statistics and p-values for each model and the critical value
- For the average model, figure of the dose-response curve
- For all significant model shapes, figures of the dose-response curve plus 90% confidence band (of the predicted shape)

The MCPMod trial analysis will be implemented by calling an R function/package within SAS. Please see [Section 10.1.2](#) for the R code to implement the MCPMod analysis.

#### **7.4.3        Supplementary analysis**

An additional analysis of the primary endpoint will repeat the primary analysis methodology (MMRM/MCPMod) specified in [Section 7.4.1](#), but under a treatment policy estimand, i.e., effectiveness/intention to treat. This estimand approach will use all available MADRS data, including data collected after any intercurrent event listed in [Table 3](#). As discussed in [Section 6.3](#), an intercurrent event of death will be handled using a hypothetical approach.

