### 7.3 HANDLING OF MISSING DATA

Every effort will be made to collect complete data at all visits.

The primary estimand of interest is the treatment effect assuming all participants remain adherent to the assigned trial medication and trial protocol using a hypothetical approach. For the primary analysis of the primary endpoint, missing data will not be imputed. Data collected after discontinuation of trial medication will be censored for the primary analysis. The mixed effects model will handle missing data based on a likelihood method under the assumption of missing at random.

For the supplemental analysis of the primary endpoint based on a treatment policy estimand, i.e. intention to treat, all available data including data collected after treatment discontinuation or other intercurrent event will be analysed.

Similar methods for handling missing data will be used for secondary efficacy endpoints, as applicable.

With respect to safety evaluations, it is not planned to impute missing values.

More details for missing data handling will be included in the TSAP, if needed.

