### Supplementary estimand approach

A supplementary analysis of the primary endpoint will use a treatment policy estimand, i.e., effectiveness/intention to treat. For patients who die during the trial, MADRS scores do not exist (rather than just being unmeasured), so that a treatment policy approach to death is not

possible. An intercurrent event of death will be handled utilising a hypothetical approach that assumes that the patient was still alive but hence stopped taking trial medication.

The rules for handling intercurrent events during the trial are summarized in [Table 3](#).

Table 3 Handling Rules for Intercurrent Events

ICE	Primary Estimand	Supplementary Estimand
Treatment discontinuation (regardless of reason)	Hypothetical	Treatment policy
Prohibited medication use	Hypothetical	Treatment policy
Change in antidepressant background/ adjunctive therapy	Hypothetical	Treatment policy
Death	Hypothetical	Not applicable

Further details on these estimand approaches are discussed in [Section 7.4.1](#) and [Section 7.4.5](#)

In addition, the number of patients reporting each type of intercurrent event will be summarized by treatment group.

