## **6.6 HANDLING OF MISSING DATA AND OUTLIERS**

Missing data will not be explicitly imputed and will remain missing except for the binary efficacy endpoints. For the continuous efficacy endpoints that are assessed over time, a restricted maximum likelihood (REML)-based mixed model repeated measures (MMRM) approach will be used, which will ensure that missing data are handled implicitly via a missing at random assumption (MAR) by the statistical model. For the binary efficacy endpoints, multiple imputation will be used, which will ensure that missing data are also handled via the MAR assumption.

Missing or incomplete AE dates are imputed according to BI standards (see “Handling of missing and incomplete AE dates”) [\(7\)](#).

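### The supplementary treatment-policy analysis reuses the missing-at-random model, so its effect may be overstated if benefit is lost after stopping and Week 6 scores are not retrieved

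*SAP*

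**What the plan says.** SAP 7.4.3 says that the supplementary analysis "will repeat the primary analysis methodology (MMRM/MCPMod) specified in" Section 7.4.1, now under a treatment-policy estimand. The one stated change is to the data: "This estimand approach will use all available MADRS data, including data collected after any intercurrent event listed in" Table 3. Protocol 7.3 is no more specific: "all available data including data collected after treatment discontinuation or other intercurrent event will be analysed".

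For scores that are still missing, SAP 6.6 has one rule for continuous endpoints: "Missing data will not be explicitly imputed and will remain missing except for the binary efficacy endpoints". The repeated-measures model is relied on instead, "which will ensure that missing data are handled implicitly via a missing at random assumption (MAR) by the statistical model". The model statement in SAP 7.4.1 is "MODEL aval = conPTuse visit*trt base*visit / ddfm=kr s".

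Table 3 in SAP 6.3 applies treatment policy to discontinuation for any reason, to prohibited medication and to a change in background therapy. For death, SAP 6.3 uses a hypothetical approach that "assumes that the patient was still alive but hence stopped taking trial medication".

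The protocol's flow chart notes and Sections 3.3.4 and 6.2.1 ask early stoppers to keep to the visit schedule or, failing that, to return at Week 6, with MADRS as the least to be done. Those who refuse everything count as having withdrawn consent.

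In SAP Table 6 the Visit 8 window runs from Day 42 to the treatment stop date plus 7 days, and later scores fall under End of Trial. The eEOT row, however, sends efficacy data collected after early discontinuation to the later visits.

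**The concern.** A treatment-policy estimand asks what happens at Week 6 whether or not drug was continued. Observed off-drug scores answer that directly. For a stopper with no Week 6 score, the answer has to come from an assumption, and the planned model supplies one that fits the other estimand. It does not know who is off drug, so it projects that person forward from their own earlier scores and the pooled course of their arm, most of whom are still taking drug. For these participants the analysis falls back towards the hypothetical assumption of the primary analysis. It also has no component that would deliver SAP 6.3's description of death as stopping medication.

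An on-drug course is hard to defend for some of them: Protocol 3.3.4.1 requires stopping for certain suicidal ideation or behaviour, and for worsening depression that needs restricted medication. If doses differ in discontinuation, the error differs by dose and bends the supplementary dose-response curve. The result could then look more robust than it is.

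**Working it through.** **Inputs.** Protocol 7.5 is redacted, so effect size, SD and dropout are not readable. The only readable planning figure is the split of 431 in the ratio 3.5:1:1:1:2:2, which sums to 10.5. It reproduces: 431 × 3.5/10.5 = 143.67 (placebo 144), 431 × 1/10.5 = 41.05 (41 each at 5, 25 and 75 mg), 431 × 2/10.5 = 82.10 (82 each at 125 mg and quetiapine). Everything below on effect, SD, stopping and retrieval is assumed.

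**Rule of thumb.** Overstatement ≈ on-drug effect × share stopping × share of stoppers without a Week 6 score × share of the effect lost.

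**Simulation.** Two arms of 40,000; Weeks 1, 2, 4 and 6; Week 6 SD 10; adjacent-visit correlations 0.70–0.75; likelihood MMRM with arm-by-visit means and a common unstructured covariance; baseline omitted. After stopping, only a Week 6 score could be observed. The model's Week 6 contrast was compared with the true treatment-policy contrast in the same simulated data. With a 3-point effect, 20% stopping in each arm and all benefit lost, the expected truth is 3 × 0.80 = 2.40 points:

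| Stoppers with a Week 6 score | Rule of thumb | True effect | MMRM | Overstatement |
|---|---|---|---|---|
| 0% | 3 × 0.20 × 1.00 = 0.60 | 2.42 | 2.98 | 0.56 |
| 25% | 3 × 0.20 × 0.75 = 0.45 | 2.44 | 2.88 | 0.44 |
| 50% | 3 × 0.20 × 0.50 = 0.30 | 2.44 | 2.71 | 0.27 |
| 75% | 3 × 0.20 × 0.25 = 0.15 | 2.36 | 2.51 | 0.15 |
| 100% | 0 | 2.38 | 2.38 | 0 |

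The true values scatter around 2.40 by simulation error. The last column is a within-run difference.

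**Other settings, 3-point effect.**
- None retrieved, all benefit lost: 0.28 with 10% stopping, 0.88 with 30%.
- None retrieved, 20% stopping, half the effect kept: 0.31.
- Effect fully kept, 20% stopping, 50% retrieved: 3.14 true against 3.16 estimated, about 0.
- Unequal stopping, 50% retrieved, active benefit lost, and a 4-point worsening after stopping in both arms: overstated by 0.68 with 10% placebo and 30% active stopping; understated by 0.17 with 30% placebo and 10% active.

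**Scale against sampling error.** With the assumed SD of 10 and no covariates, the standard error for 125 mg against placebo is 10 × √(1/82 + 1/144) = 1.38. The worst case in the table is 0.56/1.38 ≈ 0.4 standard errors.

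**Table 6.** The Visit 8 window closes at stop date + 7. For a stop on Day 35 it closes on Day 42; for a stop on Day 36, on Day 43. Read literally, a planned Day 43 MADRS from anyone who stopped before Day 36 misses Visit 8 and goes to End of Trial. The eEOT row points the other way. If the literal reading were programmed, most retrieved Week 6 scores would be lost and the analysis would move towards the first row of the table.

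**The case against.** The strongest reply is that the protocol attacks the problem at source. It wants a MADRS at an early end-of-treatment visit within 7 days of the last dose, then the usual visits or at least Week 6. If that works, the bias is small (0.15 points at 75% retrieved) or nil. The model also uses each person's own earlier scores, and retrieved off-drug scores move the arm mean. This stands, and it is why the point is conditional. It has limits: return depends on the participant's agreement, Table 6 may discard the scores that return, and the MMRM uses only Visits 3, 4, 6 and 8, so an early end-of-treatment score mapped to Visit 5 or 7 does not enter.

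Two stronger readings are tempting. A reader might infer that the effect is overstated as a matter of fact. The documents give no readable effect, dropout or retrieval figures, and the sign reversed in one plausible setting. A reader might also infer that this analysis will merely duplicate the primary result. That holds only as retrieval approaches zero: at 50% retrieved it closes (0.60 − 0.27)/0.60 = 55% of the gap between the on-drug and treatment-policy effects.

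Nor can one say that no other sensitivity analysis exists. SAP 7.4.2 and other text are redacted, and SAP 6.3 cites a Section 7.4.5 that is not visible. Finally, proof of concept and dose modelling are specified under the primary estimand; no readable decision rule uses 7.4.3, and intercurrent events will be tabulated by arm.

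**Conclusion.** The point holds in conditional form. As readable, SAP 7.4.3 is the primary missing-at-random model with post-event scores added, and nothing ties a missing Week 6 score after discontinuation to an off-drug course. The treatment-policy effect may therefore be overstated if three things hold together: benefit is lost after stopping, a material share of stoppers have no usable Week 6 score, and heavier placebo discontinuation does not offset it. With a 3-point effect, the equal-stopping settings examined give 0 to 0.88 points, the top figure needing 30% stopping, none retrieved and all benefit lost. These figures rest on assumed inputs and a simplified model. The matter is worth correcting in a supplementary analysis; it does not touch the primary test. The conflict within Table 6 stands on the text alone.

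**What to change.** In SAP 7.4.3:

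- Keep all observed scores and the planned MMRM/MCPMod.
- Beside it, add a multiple-imputation version in which MADRS scores missing after treatment discontinuation, including death as SAP 6.3 describes it, follow an off-drug course conditional on the participant's own earlier scores. Feed the pooled Week 6 means and covariance into MCPMod.
- Use retrieved-dropout imputation where data allow. Numbers may be thin: at the assumed 20% stopping and 50% return, a 41-person arm yields 41 × 0.20 × 0.50 ≈ 4 such participants. Otherwise use reference-based imputation (jump to placebo), and label it an assumption. Protocol 3.3.3 and 4.2.2.1 require the background dose to be held only until the end of trial or end of treatment, so stoppers need not resemble the placebo arm.
- State what is assumed for scores missing after the other two Table 3 events, since those participants may still be on trial drug.
- Reconcile the Visit 8, eEOT and End of Trial rows of Table 6 for this analysis, so that it is clear whether a Week 6 MADRS from an early stopper counts as Visit 8.

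The cost is SAP wording and modest programming, since SAP 7.5.2.1 already multiply imputes MADRS totals. The supplementary estimate will probably be somewhat more conservative.
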